## 7 CORRELATIVE/SPECIAL STUDIES:

Several studies listed in this section are not necessarily research tests but they have been outlined below as the information obtained from following tests may not be needed to determine objective response (primary endpoint of the study) while they may be helpful in clinical care of the patient. Informed consent must be obtained prior to obtaining research studies [any tissue specimen, biopsies, research blood draws, and DCE-portion of MRI].

**7.1 Measure serum tumor markers (calcitonin and CEA) pre-, during-, and post-treatment to correlate with disease response.**

This will be done in all the patients participating on the study as it is considered standard of care. This will be done pre-treatment, every 16 weeks during treatment and post-treatment [within 2-4 weeks after last dose of sorafenib (BAY 43-9006)]. All the centers participating in this study perform calcitonin and CEA routinely as a part of standard clinical care.

In addition to drawing samples for serum calcitonin and CEA at the baseline, extra 10-mL of blood (research blood draw) will be drawn in red top tube on ice at pre-study visit. Serum will be separated, aliquoted in 0.5 mL/tube and stored for possible future re-measurement of calcitonin and/or CEA. Such frozen samples will be utilized if clinical laboratory changes the calcitonin and/or CEA assays while patient is on study, to avoid inter-assay variation. In such cases, such baseline sample may be re-run concurrently with specimen drawn during treatment.

**7.2 Perform a nuclear medicine functional imaging F-18 fluorodeoxyglucose positron emission tomography (PET) scan] pre-, and during-treatment.**

PET scans are not required as a part of this research study. Per protocol, PET scans are not used for response assessment. PET scans may be done in any patient on the study as clinically indicated pre-treatment and every 16 weeks during treatment. This will be determined by the treating physician.

**7.3 Perform a dynamic-contrast enhanced magnetic resonance imaging (DCE-MRI) pre-, and during-treatment to correlate change in tumor permeability and vascularity with tumor response.**

All the centers participating in this study perform MRI routinely as a part of standard clinical care for the cancer patients. These centers also have capacity to perform DCE-MRI. While DCE-portion of this test is considered research, MRI is considered a standard imaging for patients with medullary thyroid carcinoma. All centers participating in the study will use a standard uniform acquisition protocol for DCE-MRI scan (see Appendix C for the details). Digital images will be transferred to [name] OSU imaging laboratory for central reading. DCE-MRI scans are performed as a part of laboratory correlative studies only and the results will not be used to assess the response.

**DCE-MRI scan will be preferred in at least 16 patients entered on the Arm A and at least 16 patients entered on Arm B of the study except under the following circumstances:**

Patients who have:

- Cardiac pacemaker
- Other ferromagnetic metal implants not authorized for use in MRI such as some types of cerebral aneurysm clips
- Claustrophobia not helped by pre-medications
- Obesity (exceeding the equipment limits)
- Following circumstances exist:
  - In case, MRIs are not suitable for evaluating response per RECIST criteria
  - Investigator's disapproval
  - Funding for the research part of DCE-MRI is not sufficiently available

**DCE-MRI may be performed for the remaining patients enrolled on Arms A and B of the**

**study per investigator's discretion.**

**Time points:** Performed pre-therapy (within 4 wks prior to treatment), at 8 weeks on therapy. DCE-MRI scans at the time points beyond 8 weeks (at every 8 week interval while on the study and at off study visit time point) may be done per investigator's discretion.

**Note:** MRI scans will be continued to be utilized to measure response.

#### **7.4 Pharmacogenomic studies:**

We will procure PBMCs from all the patients enrolled on the study. Pharmacogenomic studies will be performed in all the patients if any clinical responses are observed on this trial. We will examine for selected polymorphisms of genes influencing sorafenib (BAY 43-9006) metabolism and/or resistance genes that may predict response or toxicity. These changes will be correlated with toxicity and clinical response to therapy.

**Blood will be drawn for all the patients enrolled on the study.**

**Sample collection and shipping:** 20 ml peripheral blood in heparinized tube (usually solid green top tubes) will be collected, kept at the room temperature till shipped on the same day of collection (see Appendix B for shipping instructions). Blood specimens will be collected from all patients and PBMCs will be isolated.

**Time Points:** Performed pre-therapy (within 4 weeks prior to registration).

#### **7.5 Assess the degree of Ras-MAPK signaling inhibition, and vascular endothelial growth factor (VEGF) expression in the tumor and clinical response. (Maximum of 24 patients to participate)**

Perform MAP kinase and AKT phosphorylation assay by immunohistochemistry to evaluate the degree of RET-Ras-MAPK signaling inhibition by sorafenib (BAY 43-9006) in tumor biopsies. Given that sorafenib (BAY 43-9006) also inhibits VEGFR, we will evaluate VEGF expression in tumor biopsies to correlate with DCE-MRI parameters and with clinical response when possible.

**These tests will be performed in any patients on Arm A or B of the study who has biopsiable disease and is willing to undergo biopsies for research purposes.**

**Biopsies will not be performed under one of the following circumstances:**

- Investigator's disapproval
- Funding for the biopsies is not sufficiently available
- Patient refuses to undergo the procedure.

**In such cases biopsies may be performed pre-treatment (within 4 weeks prior to starting treatment) and at 8 wks on treatment. Post-treatment (within 4 wks after last dose of treatment) biopsies in these patients may be performed per investigator's discretion.** Please note that the CT or MRI, DCE-MRI, and PET scan that might need to be done at these time points should be done prior to doing biopsy procedure. No specific time interval is necessary between these imaging studies and biopsy.

**Sample collection and processing:** Fine needle aspiration (FNA) biopsies (using 18-21 gauge needle) of the tumor (ie: either cervical lymph nodes or bulky bony or lung or liver metastasis) will be performed under imaging guidance or blindly depending on the location and size of the tumor.

Fine needle aspirated material will be collected in the tubes containing RPMI media. No direct smears slides will be made from FNA. Using Autocyte PREP system standard protocol, slides will be prepared using CytoRich® Red (Tripath Imaging) cytological preservative. The actual slides used will be PLUS slides; as these are precoated that facilitates the cells staying on the slides during processing. At least 8 unstained slides will be prepared using the standard protocol. Two slides will be stained with PapStain for cytologic diagnosis so that we verify that tumor was indeed present in the FNA specimen.

**Principle of Autocyte PREP system:** The AutoCytE PREP System converts a liquid suspension of a cell sample into discretely stained, homogenous thin-layer of cells while maintaining diagnostic cell clusters. The process includes cell preservation, randomization, enrichment of diagnostic material, automated pipetting, sedimentation, and discrete staining portions of the process. The AutoCytE PREP presents a wellpreserved population of stained cells present within a 13mm diameter circle. Using this system, we have been able to perform immunohistochemistry studies on specimens prepared from FNA material in our ongoing CTEP- sponsored phase II trial (NCI 6609).

All stained and unstained slides will be shipped to [name] at the OSU (see [Appendix B](#) for shipping instructions) who then will transfer batched specimen to [name] laboratory.

**Methods:** Studies on unstained slides will be processed at [name] laboratory at the OSU. **Immunohistochemical staining** Sections will be dewaxed, soaked in alcohol and after microwave treatment in antigen unmasking solution for 10 min incubated in 3% hydrogen peroxide for 15 min to inactivate endogenous peroxidase activity. Sections will be incubated at 4°C overnight with anti- phospho-Akt (dilution 1:100), with anti-Ret (C-19) (dilution 1:100), with anti-p44/42 MAP kinase (dilution 1:100), with anti VEGF (dilution 1:100). Immunostaining will be performed by use of the Vectastain Universal Quick kit according to the manufacturer's instruction. Peroxidase staining will be revealed with 3, 3 - diaminobenzidine. Negative control will be applied by omission of antiserum. Results will be interpreted independently by three blinded investigators and scored for the presence or absence of staining. Scoring will be compared between the three investigators independently and agreement between two of the three investigators will be required for a positive result to be assessed.

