### 1.2 Secondary Objectives:

- 1.2.1 To assess toxicity of sorafenib (BAY 43-9006) in patients with metastatic medullary thyroid carcinoma.
- 1.2.2 Measure serum tumor markers calcitonin and carcinoma embryonic antigen (CEA) pre-, during-, and post-treatment to correlate with disease response.
- 1.2.3 Correlate nuclear medicine functional imaging [F-18 fluorodeoxyglucose positron emission tomography (PET) scan] data obtained at pre-, during- and post-treatment with tumor response.
- 1.2.4 Correlate dynamic-contrast enhanced magnetic resonance imaging (DCE-MRI) data obtained at pre-, during- and post-treatment with changes in tumor permeability and vascularity with tumor response.
- 1.2.5 Perform pharmacogenomic studies on procured PBMCs if clinical responses are observed.
- 1.2.6 To correlate between the degree of Ras-MAPK signaling inhibition and vascular endothelial growth factor (VEGF) expression in the tumor and clinical response.
- 1.2.7 To correlate between the presence and type of RET gene defects in tumor and clinical response.

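### Section 7.5 scores tumor staining only as present or absent, so the biopsies cannot supply the graded degree of Ras-MAPK inhibition that objective 1.2.6 needs

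*Combined protocol and SAP*

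**What the plan says.** Objective 1.2.6, repeated in section 11.3, reads: "To correlate between the degree of Ras-MAPK signaling inhibition and vascular endothelial growth factor (VEGF) expression in the tumor and clinical response". Section 7.5 opens with the matching laboratory purpose: "Perform MAP kinase and AKT phosphorylation assay by immunohistochemistry to evaluate the degree of RET-Ras-MAPK signaling inhibition". Fine needle aspirates may be taken before treatment and at 8 weeks, with a post-treatment sample at the investigator's discretion. Participation is voluntary, depends on funding and investigator agreement, and is capped at 24 patients over both arms.

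The 7.5 Methods then describe the reading. Three blinded investigators interpret the slides independently, and results are "scored for the presence or absence of staining". The combining rule is that "agreement between two of the three investigators will be required for a positive result to be assessed". The antibody list names "anti- phospho-Akt (dilution 1:100" for one target and "with anti-p44/42 MAP kinase (dilution 1:100" for another; Ret and VEGF antibodies complete it.

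Section 11.3 lists ERK phosphorylation and pathway inhibition among the markers with little known variability, and plans to estimate variance from the first eight patients. It gives no scale, threshold or test for the staining results.

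**The concern.** The objective asks how much the pathway is inhibited. The method records a yes/no state at each visit. A yes/no state cannot be turned into a degree at the analysis stage, because the graded information was never written down.

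The patients in this substudy undergo needle biopsies for research. Some of the sites named are lung, liver or bone metastases. If the reading is done as written, the material yields a proportion of tumors that lose staining, and the correlation set out in 1.2.6 cannot be carried out in its stated form. The missing phospho qualifier adds a second uncertainty about what the MAPK stain represents.

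**Working it through.** The documents give no sample size, effect size or power for 1.2.6, so there is no planned figure to reproduce. The check is mainly a comparison of sections.

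**1. What is wanted and what is recorded.**

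| Item | Objective 1.2.6 and opening of 7.5 | 7.5 Methods |
|---|---|---|
| Quantity | Degree of inhibition | Staining present or absent |
| Readout | Phosphorylation of MAP kinase and AKT | Phospho-Akt; p44/42 MAP kinase without a phospho qualifier |
| Combining readers | Not stated | Two of three must agree for a positive |
| Positivity threshold | Not stated | Not stated |
| Definition of inhibition between visits | Not stated | Not stated |

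**2. Patterns available per marker and patient.** Two yes/no reads give 2 × 2 = 4 patterns: +/+, +/−, −/+ and −/−. Only +/− can count as inhibition. A tumor negative at baseline can produce only −/+ or −/−, so it cannot show inhibition.

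**3. Dependence on the unstated threshold.** Let B be the true baseline staining, W the week-8 staining and c the level at which the readers call a slide positive.
- If c ≤ W, the pair is +/+ (no change).
- If W < c ≤ B, the pair is +/− (inhibition).
- If c > B, the pair is −/− (inhibition cannot be seen).

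Take a 50% fall as an assumed example, so W = B/2. It is recorded as inhibition only if c lies between B/2 and B. The plan does not say where c lies, so the same biological change can be recorded in any of three ways.

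**4. The eight-patient variance step in 11.3.** For a yes/no result with proportion p, the variance is p(1 − p) and is fixed once p is known. A separate variance estimate therefore adds little for this marker.

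**5. The reagent.** The Schema lists MAPK and AKT phosphorylation, 7.5 opens with a phosphorylation assay, and 11.3 refers to ERK phosphorylation. Against these three places, the antibody list puts phospho before Akt and omits it before p44/42.

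**6. Slides.** The 7.5 Methods provide at least 8 unstained slides, and two slides are Pap-stained. If those two come from the eight, 8 − 2 = 6 remain. Four antibodies and one negative control leave 6 − 4 − 1 = 1. A graded reading of the same slides needs no more material; an added total-p44/42 stain would use the last one.

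**7. Illustration of what a yes/no scale can cost.** All effect sizes here are assumptions. Inhibition is taken as normal with equal SD, 24 patients are biopsied, and responders are shifted by 1.0 or 1.5 SD. The yes/no cut lies halfway between the group means, alpha is 0.05 two-sided, and each row uses 4,000 simulated trials. Seven responders corresponds to the 30% target rate (0.30 × 24 = 7.2).

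| Responders | Shift | Graded, t-test | Graded, Mann-Whitney | Yes/no, Fisher |
|---|---|---|---|---|
| 5 | 1.0 SD | 49% | 43% | 32% |
| 5 | 1.5 SD | 81% | 76% | 62% |
| 7 | 1.0 SD | 57% | 53% | 29% |
| 7 | 1.5 SD | 90% | 87% | 62% |

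This cuts a single normal variable and does not model two separate yes/no reads. Part of the gap also reflects the conservatism of Fisher's test. It shows direction only.

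**The case against.** The strongest reply is that this is a wording mismatch in an optional substudy. Paired yes/no reads still carry information, namely the proportion of patients who lose staining. Section 11.3 already warns that numbers may be too small for the biological correlates. A graded score would not cure that: in the illustration it reaches only 43% to 57% power at a 1.0 SD difference. The biopsies also serve the VEGF and DCE-MRI correlation. All of this stands and limits the weight of the point, but it does not supply the degree that 1.2.6 asks for.

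Four stronger readings are tempting, and the documents do not support them.
- *The MAPK stain measures total protein.* No clone, supplier or catalogue number is given, and three places describe phosphorylation. A shorthand reagent name is the likelier explanation.
- *Only complete loss of staining is detectable, or a 50% fall always scores as zero.* That assumes a threshold near zero, and none is stated.
- *24 patients act like about 15.* The figure comes from the efficiency of a median split of a normal variable, 2/π = 0.637, and 0.637 × 24 = 15.3. The plan compares two yes/no reads with no known distribution or cut, so the benchmark does not transfer.
- *A false finding of no inhibition is likely.* The documents give no baseline positivity, effect size or assay variance from which to judge this.

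**Conclusion.** The point holds on the text alone. The objective and the opening of 7.5 require a degree of inhibition; the 7.5 Methods record a yes/no state without a threshold, and neither 7.5 nor 11.3 supplies a graded scale. As written, the plan can report whether a tumor crosses from positive to negative between pre-treatment and week 8, and no more. The reagent wording is a secondary clarification, probably an omission.

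The size is modest. One of seven secondary objectives is affected, in a voluntary substudy of at most 24 patients. The primary endpoint rests on RECIST imaging and is untouched. The structural conclusion needs no numerical assumption. Any gain in efficiency from a graded score is illustrative. This should be corrected because the remedy is cheap and the biopsies are done for research.

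**What to change.** In the 7.5 Methods:
- Have the same three blinded readers record a graded score for each slide, for example intensity and percent of positive cells, and average it over readers.
- Define inhibition as the within-patient change in that score from pre-treatment to week 8.
- Correlate the change with clinical response, the outcome already stated in 1.2.6, and name the test in 11.3.
- Keep the present/absent call as a secondary summary, with its threshold stated.
- Write phospho-p44/42 in the antibody list, to agree with the Schema, the opening of 7.5 and 11.3.

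If graded scoring is not feasible on fine needle aspirates, reword 1.2.6 and the matching line in 11.3 to loss of staining (yes/no). That also removes the mismatch.

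The cost is a new score sheet, slightly longer reading and some reader variability in the graded score. No extra biopsies, slides or readers are needed. A total-p44/42 reference stain is best left optional, since it could exhaust the slides.

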## 7.6 Assess the presence and type of RET gene defects in the tumor to correlate with clinical response.

As the presence of RET gene mutations in patients with metastatic sporadic medullary thyroid carcinoma is highly variable but on average about 25%, we plan to examine the presence and type of such gene defects in our patient population while treating them with sorafenib (BAY 43-9006) that inhibits the downstream signaling pathway for RET.

**As patients on Arm A are expected to have germ-line mutations in RET, collection and studies on tumor tissue blocks may not be necessary in those patients.** In this group of patients, we will have RET germ-line mutation information available from the genotyping

studies performed in the peripheral blood (see [section 7.7](#)).

**All patients on Arm B on the study will have this test performed except under the following circumstances:**

- Tissue block is not sufficient for research purposes.
- Tissue block is not transferable for research purposes.

**Sample collection and shipping:** There is no new biopsy performed for this test. The tissue block preserved routinely at clinical pathology laboratory of previously performed thyroid cancer biopsy/surgery will be obtained and shipped to [name] at the OSU (see [Appendix B](#) for shipping instructions).

**Time point:** Anytime prior to registration on the study.

**Methods:** Ten micron/slice will be cut from the tumor paraffin tissue block and such 3-4 unstained slides will be used for isolating tumor DNA. H&E slides will be prepared to verify pathologic diagnosis. Tumor DNA will be isolated in [name] laboratory at the OSU.

**DNA extraction:** After microdissection of tumor on slides, DNA will be extracted using QI-Amp DNA mini kit (Qiagen SA) according to the manufacturer's instruction. All PCR products will be electrophoresed on 3% agarose gel in TAE buffer and stained with ethidium bromide.

RET mutation studies will be performed in [name] laboratory at the OSU using standard protocol for RET genotyping.

#### **7.7 Assess the presence and type of RET gene defects in the peripheral blood to correlate with clinical response.**

RET genotyping in peripheral blood is a clinical test that is standard of care in all patients with medullary thyroid carcinoma. Each participating center will use their clinical laboratories to perform such RET genotyping tests.

This test will be sent out to the clinical laboratory (5 mL blood in one purple top/EDTA tube) in all the patients enrolled on the study during their pre-study visit unless the RET mutation analysis report from previously performed analysis is available.

## 8 STUDY CALENDAR

	Pre-therapy a	Course I (subsequent courses as course I b )		Off-therapy c
		Week 4 b	Week 8	
Sorafenib (BAY 43-9006) d				
Patient diaries		X	X	X
History/Physical Exam	X	X	X	X
Vital signs/Weight	X	X	X	X
Blood pressure monitoring	Once a week till stable or at least for the first 4 weeks.			X
Adverse Event Evaluation		X	X	X
CBC w/diff, platelets	X	X	X	X
Serum chemistry e	X e	X e	X e	X e
Serum β-HCG f	X f			
CT or MRI scan of neck/chest/abdomen g	X g		X g	X g
Serum Calcitonin and CEA	X		X	X
Following tests may be done in selected group of patients ONLY. See Sec7.0 for the details.				
10-mLblood for procurement of serum ( Section 7.1 )	X			
PET scan ( Section 7.2 ) h	X		X	X
DCE-MRI scan ( Section 7.3 )	X		X	X i
20-mLblood for plasma and PBMCs ( Section 7.4 )	X			
FNA biopsy of the tumor ( Section 7.5 )	X k		X k	X j
Paraffin tumor tissue block ( Section 7.6 )	X			
RET genotyping to clinical lab ( Section 7.6 )	X			
a: Pre-therapy evaluations are to be conducted within 10 days prior to administration of sorafenib (BAY 43-9006) except imaging studies, research blood draws, and tumor biopsies that should be done within 4 weeks prior to the start of therapy.				
b: Week 4 evaluations may be done at local doctor's office. However, AE eval must be by research staff via phone interview with the patient and principal investigator must sign off on adverse event data forms within 36 hours of the phone interview.				
c: Off-therapy evaluations are to be conducted within 4 weeks after last dose of sorafenib (BAY 43-9006) treatment. Serum calcitonin and CEA, CT/MRI scans will be optional if a patient received sorafenib (BAY 43-9006) for ≤4 weeks.				
d: Oral sorafenib (BAY 43-9006) will be given with 250 ml (about 8 ounces) of water at the dose of 400 mg BID.				
e: Sodium, Potassium, Chloride, Bicarbonate, Creatinine, BUN, Glucose, Phosphorus, Total protein, Albumin, Total bilirubin, S GOT (AST), SGPT (ALT), Alkaline phosphatase, LDH.				
f: Pregnancy test (sensitivity of at least 50 mIU/mL) will be performed for all women of childbearing potential before beginning sorafenib (BAY 43-9006).				
g: CT or MRI scans as determined by investigators to assess the response per RECIST criteria.				
h: PET scans are performed only as clinically indicated as determined by treating physicians.				
i: Research blood draws and tumor biopsies will not be required in subsequent courses.				
j: Optional per investigator's discretion.				
k: If patient has biopsiable disease and agrees to have biopsies for research purpose.				
l: After six months, we will eliminate week 4 visits and all associated testing at week 4 of the each course. Patients will return to OSU every 16 weeks for an evaluation visit.				

